5. BACKGROUND*

After 40 years of considering gastrointestinal bleeding as upper or lower and largely ignoring the small intestine, there is accumulating evidence that the conventional approach to the assessment of NHGIB could be improved by early deployment of a video capsule as the first diagnostic test. Currently, video capsule endoscopy is considered the gold standard diagnostic test for small intestinal bleeding after upper and lower endoscopy. However, we feel that video capsule endoscopy is an underutilized, minimally invasive tool that can improve rates of detection, minimize patient discomfort, and shorten the length of hospital stay for many patients. In a recent study at UMass of 336 patients who presented to the ED with complaints of gastrointestinal bleeding only 36 patients (10.7%) were given a video capsule during their stay.¹

Traditionally, in patients with hematemesis, upper endoscopy has been the diagnostic and therapeutic modality of choice. However, recent data from a randomized clinical trial by Sung et al suggests that when video capsule endoscopy is used as the primary diagnostic tool, the investigators were able to safely define those patients that require admission from those that can be discharged for later follow-up². In this cohort, 30% of patients could be safely discharged and undergo endoscopy, if necessary within 48 hours, as an outpatient. This data is consistent with our internal epidemiological data from UMass where nearly 30% of patients who were admitted did not receive any endoscopic evaluation as in-patients.

Similarly, in a randomized controlled trial, we have recently shown that patients with NHGIB may benefit from early VCE. In this population, the detection of active bleeding with video capsule as the first procedure was 63% compared with 27% for the standard of care approach. We did not demonstrate a significant reduction in length stay since this was not part of the trial design. No attempt was made to change physician behavior. The study was too small to demonstrate a reduction in procedures, but there was a modest reduction in healthcare costs despite the addition of the video capsule. We encountered no adverse events in the study. Readmission rates were not significantly reduced but there were no readmissions in the capsule group for G.I. bleeding where there were four in the standard of care group.

Our hypothesis is that both signs and symptoms provide poor localization as to the origin of bleeding in NHGIB. Data from our previous study suggests that the ingestion of a video capsule in the emergency department could quickly and non-invasively provide clinicians accurate data as to the origin of the bleeding. This information could provide a guide to further management of the patient. Video capsule endoscopy is able to visualize bleeding in the esophagus, stomach, duodenum, small intestine and right colon, thereby eliminating the guess work of deciding which endoscopic approach to use.

We plan to use the clinical decision unit for two reasons. This unit provides an ideal site for the early safe deployment of a video capsule or initiation of a standard of care workup for either or NHGIB. Second, in those patients who are demonstrated not to be bleeding

INVESTIGATOR STUDY PLAN - H00015196

in either group by capsule endoscopy or standard of care workup may be discharged home safely without being admitted, thereby saving significant costs. It is known that 80% of patients stop bleeding spontaneously. Thus, the earlier they are examined the more likely the origin of the bleeding is likely to be found and appropriate management instituted

The use of capsule endoscopy has been approved by the FDA since 2001 for small intestinal bleeding obscure GI Bleeding. It is very safe, no deaths associated with its use have been reported. More than 3 million capsules have been deployed and obstruction and perforation are extremely rare.

Interest in the broader use of VCE is accumulating. In 2004 Sachdev et al reported a pilot study on the use of early use of VCE in acute NHGIB. This showed a 50% reduction to time to diagnosis in 24 patients. More recently studies of VCE deployed in the ED, in patients with upper GI bleeding showed improved management. Our group recently demonstrated that the closer a video capsule is performed to the time of bleeding the higher the likelihood of locating the sources and the higher the therapeutic intervention rate.³

This protocol is logical step to prospectively examine this concept in a large randomized prospective trial for both H and NHGIB. The questions are, can early capsule intervention decrease time to diagnosis, numbers of procedures, admission rate and hospital length of stay in patients with H and NHGIB.

References:

6. INCLUSION AND EXCLUSION CRITERIA*

Inclusion Criteria:

- Age greater than 18 years old

INVESTIGATOR STUDY PLAN - H00015196

- New onset of hematemesis, melena or hematochezia
- Able to sign consent
- Hemodynamically stable (i.e. blood pressure >100/60 or pulse <110 at the time of consent)
- ED must plan to admit patient to the hospital or Clinical Decision Unit.
- If patients have pacemakers and/or ICD they will be placed on telemetry.

Exclusion criteria:

- Adults unable to consent
- Individuals who are not yet adults (infants, children, teenagers)
- Pregnant women
- Prisoners
- Prior history of gastroparesis
- Prior history of gastric, or small bowel surgery
- Prior history of inflammatory bowel disease
- Concern for infectious colitis
- Evidence of dysphagia at the time of presentation
- Presence of small amounts of bright red blood per rectum
- Allergy to metoclopramide or erythromycin
- Code status of DNR/DNI or CMO
- Prior history of abdominal radiation
- Abdominal pain suggesting an acute abdomen or obstruction. In clinical practice, only patients with crampy abdominal pain due to Crohn's disease, previous intestinal surgery and a previous history of radiation therapy require a patency capsule or CT enterography, before capsule endoscopy.
- Patients who cannot undergo surgery

Subjects who do not speak English may be included if an IRB-approved short form is available for use in their language and interpretation services are available.

7. **STUDY-WIDE NUMBER OF SUBJECTS***

See #25.

8. **STUDY-WIDE RECRUITMENT METHODS***

See #24.

9. **STUDY TIMELINES***

- The participation of individual subjects in this study will be approximately 31-40 days (the length of their hospitalization plus an additional thirty days for follow up).
- The duration anticipated to enroll all study subjects is about 24 months.

INVESTIGATOR STUDY PLAN - H00015196

- The estimated date for the investigators to complete this study and for data analysis is 3 years.

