4. OBJECTIVES*

- 1) The objectives of this study are to compare the efficacy of video capsule endoscopy (VCE) as first line vs the standard of care workup of H [upper endoscopy] and NHGIB by endoscopy [upper, lower and other tests] in the rate of detection of active bleeding in patients admitted to the clinical decision unit (CDU). We propose to examine differences in time to detection of active bleeding, diagnosis, reduction in numbers of procedures, hospital costs and length of stay between a conventional workup protocol and our proposed protocol of early capsule endoscopy deployment. All patients in the SOC group will be admitted to the

INVESTIGATOR STUDY PLAN - H00015196

hospital. These will be compared to those in the VCE first group who are stable and may be discharged from the CDU directly.

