11. PROCEDURES INVOLVED*

Screening

- Patients presenting to the Emergency Room with H or NHGIB (defined as hematemesis, or melena or hematochezia respectively or severe anemia) will be identified by a member of the ED staff and triaged to the CDU for stable patients or ICU for unstable patients.

Once a subject is identified a page will be sent to a member of the research team (i.e, research staff member, GI fellow on call, or GI attending on call) from the CDU. In addition to this, the clinical research coordinator and or GI fellow will screen the Emergency Department triage software for patients who are listed as having NHGIB. Based on prior experience of our randomized trial we expect for every 3 patients asked to participate in the study, there will be 1 patient who agrees to participate. In the Emergency Department study already cited, the Emergency Department at UMass sees about 350 patients annually for GI bleeding. Of these patients, approximately 230 patients have NHGIB and 120 have hematemesis. Given the 3:1 screening ratio, we would expect approximately 40 to be enrolled for the H and 40 patients for the NHGIB patients every year who agree to participate in the study. In 24 months, we would expect to recruit up to 160 patients to our study, 80 for the H and NHGIB respectively. Once a subject is identified the subject will then be seen and examined by the GI fellow and attending as per standard of care and asked to participate in the study.

[figure not shown]
Randomization:

- If inclusion/exclusion criteria are met, the consent discussion takes place and only if the subject agrees and consent is obtained, then the subject is randomized to the “Early Capsule Group” or “Standard of Care Group.” All patients in the “Early Capsule group” will receive the video capsule. A few of the patients in the “Standard of Care Group” may receive the capsule as indicated by what is considered the standard workup.

INVESTIGATOR STUDY PLAN - H00015196

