- We will assign patients to study ID numbers consecutively by the order of which they are enrolled in our study. For the Randomization Process we will be utilizing a random sorting generator to assign integers in a random order, corresponding to study IDs which allows researchers to randomly assign study participants into specific study groups. The same process would apply to the H and NHGB groups, but each of these groups will have separate randomizations. Assignments are put into a mail merge, locked with a password, and printed, then put into a sealed, security envelope, which is sealed with a Study ID sticker. The Randomization Scheme will allow us to attach particular Study ID numbers randomly to particular groups based on our criteria to have 40 subjects in the early capsule group and a comparable number in the Standard of Care SOC workup arm for both the H and NHGIB groups. The envelope is only opened once all entry criteria have been met and the subject will be assigned a group/arm. Subjects with a Study ID ending in 1-80 will be enrolled in the H group. Subjects with a Study ID ending in 100-180 will be enrolled in the NHGIB group.
- We plan to enroll up to 160 subjects in our study. 40 subjects will be randomized to the “early capsule” deployment group and 40 in the SOC arm for H patients. A similar allocation will apply to the NHGIB group with 40 patients in each arm. This means that this group of subjects will have a VCE deployed as soon as possible after presentation to the ED and CDU, once the consent process has taken place, eligibility has been confirmed, and the subject has met the standard of care guidelines for preparation before capsule ingestion. Standard preparation for capsule ingestion means that a patient cannot eat for 10 hours prior to deployment of the capsule. Therefore, patients in our study will be asked when they had last eaten. If patients report that they have not eaten anything over the past 10 hours we will deploy the capsule immediately. If, however, patients say that they have eaten something over the past 8 hours we will take note of when they believe they last ate and will deploy the capsule 8 hours after the time that they last ate. In our previous ED study, no patients in the early capsule arm had food in the stomach on capsule examination.

INVESTIGATOR STUDY PLAN - H00015196

[figure not shown]

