22. SETTING

Initial screening of subjects will be performed in the Emergency Room at the UMass Memorial Medical Center – University Campus-Patients – if hemodynamically stable will be transferred to the CDU. Review of video capsule recordings will occur in the GI endoscopy clinic on the same campus. Endoscopic procedures will either be performed in the CDU or adjacent endoscopy unit.

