30. CONSENT PROCESS

Consent will take place in the Emergency Department or the Clinical Decision Unit. Study staff will follow [HRP-802 INVESTIGATOR GUIDANCE: Informed Consent](#). Subjects will be given as much time as they require before making a decision to participate in the study. The time provided for discussing the consent process with subject will be 15 minutes or greater as the subject requires. Only the listed study staff members will be involved in the consent process.

In order to minimize the possibility of coercion during the consent process, potential subjects will be notified that their care will not be altered in any way if they choose to provide or not provide consent.

If a potential participant does not speak English, but both an IRB-approved short form and appropriate interpreter services are available, non-English speaking subjects may be recruited for this study.

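### The stability criterion joins its two limits with 'or', so it excludes only patients who fail both; the connective should be 'and'

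*Protocol*

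**What the plan says.** The inclusion list in Section 6 of the protocol contains one hemodynamic requirement: "Hemodynamically stable (i.e. blood pressure >100/60 or pulse <110 at the time of consent". No exclusion criterion in that section mentions low blood pressure or a fast pulse.

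Other sections rely on the word 'stable' without giving figures:

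- Section 4 (Objectives) describes patients in the "VCE first group who are stable and may be discharged from the CDU directly".
- Section 11 (Screening) has patients "triaged to the CDU for stable patients or ICU for unstable patients".
- Section 22 (Setting) says that patients "if hemodynamically stable will be transferred to the CDU".

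The DSMB charter, supplied as the SAP, gives no hemodynamic limit either. On the order of events, Section 30 states that "Consent will take place in the Emergency Department or the Clinical Decision Unit", and Section 11 (Randomization) that "The envelope is only opened once all entry criteria have been met".

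**The concern.** The parenthesis opens with 'i.e.', so it reads as the meaning of 'hemodynamically stable', and 'or' makes either limit sufficient. That connective suits a definition of instability (low pressure or fast pulse). Attached to limits that describe stability, it reverses the protection: a patient can be hypotensive, or markedly tachycardic, and still satisfy the criterion.

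Two things are at stake.

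- **Safety.** The capsule arm is built for patients who can wait. The capsule is the first test. A patient who has eaten recently waits out a fasting interval (Section 11 gives both 8 and 10 hours). A capsule that is slow to leave the stomach may lead to a dose of metoclopramide or erythromycin, and Section 16 lists hypotension and tachycardia among the effects of metoclopramide. Direct discharge from the CDU is also foreseen. These steps suit a patient who meets both limits.
- **Population.** One screener may apply 'or' literally and another may read it as 'and'. They would then decide differently on the same patient, and the enrolled population is not clearly defined.

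**Working it through.** **Inputs** (protocol Section 6). Let A = blood pressure above 100/60, read as systolic >100 and diastolic >60. Let B = pulse <110. Both are assessed at the time of consent. The plan gives no figure to reproduce here, and no sample-size or error-rate calculation depends on this rule.

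**Step 1: logic.** As written, eligible = A or B, so excluded = not A and not B. With the other connective, eligible = A and B, so excluded = not A or not B.

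| A: pressure limit met | B: pulse limit met | Eligible under 'or' | Eligible under 'and' |
|---|---|---|---|
| yes | yes | yes | yes |
| yes | no | yes | no |
| no | yes | yes | no |
| no | no | no | no |

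'Or' admits three of the four combinations, two of which fail a stated limit. 'And' admits one. These are logical cases, not patient counts.

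**Step 2: worked patients** (hypothetical readings).

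| Reading | 'or' | 'and' | systolic >100 and pulse <110 |
|---|---|---|---|
| 80/45, pulse 100 | eligible | not eligible | not eligible |
| 120/75, pulse 140 | eligible | not eligible | not eligible |
| 85/50, pulse 125 | not eligible | not eligible | not eligible |
| 130/58, pulse 80 | eligible | not eligible | eligible |
| 120/75, pulse 80 | eligible | eligible | eligible |

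The first two rows are the problem. The fourth shows that a bare swap to 'and' also removes a patient whose only failure is a diastolic value just under 60; a systolic-only limit keeps that patient.

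**Step 3: does another step close the gap?**

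- Sections 4, 11 and 22 use 'stable' without figures, so a reader who wants a number is sent back to Section 6.
- CDU placement is not an entry requirement in Section 6, which also accepts a plan to admit to hospital.
- Staff also "screen the Emergency Department triage software for patients who are listed as having NHGIB", and consent may be taken in the ED, before any CDU transfer.
- Under Section 23, fellows and residents review the written criteria with the patient, and the envelope is opened once those criteria are met. A patient who passes the 'or' rule can therefore be randomized.

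**Step 4: size.** The documents give no failure rates. Suppose, purely as an illustration, that a proportion a fails the pressure limit and b the pulse limit, independently, each between 5% and 20%:

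- 'or' excludes a × b: 0.05 × 0.05 = 0.25% up to 0.20 × 0.20 = 4%.
- 'and' excludes a + b − a × b: 0.05 + 0.05 − 0.0025 = 9.75% up to 0.20 + 0.20 − 0.04 = 36%.

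The range is wide, and independence is itself doubtful in bleeding patients, in whom low pressure and fast pulse tend to occur together. It shows only that the choice of connective could matter in practice.

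**The case against.** The strongest reply is that no clinician would enroll the patients in the worked examples. The operative words are 'hemodynamically stable', and the authors use 'i.e.' loosely: Section 11 (Review and Follow-Up) introduces the same list of procedures once with 'e.g.' and once with 'i.e.'. Unstable patients are triaged to the ICU. The gastroenterology fellow and attending examine each patient before asking for participation. Section 29 says that recruited patients require CDU admission, and Section 22 allows CDU transfer only for stable patients. After a capsule that shows no blood, the patient is observed for up to 23 hours before discharge is considered, and a DSMB reviews adverse events. Figures omitted from the text available here might also carry thresholds.

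Much of this is fair as a description of practice, and it lowers the likely harm. It does not repair the criterion. The CDU condition turns on the same word that only Section 6 defines numerically; triage and examination supply no limit; and observation and DSMB review act after randomization. Loose use of 'i.e.' elsewhere does not tell a screener to disregard a stated inclusion rule.

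A second reply concerns recruitment, and part of it stands. The hematemesis projection has no slack: 120 patients a year × 1/3 × 2 years = 80, exactly the number needed. It allows nothing for exclusions of any kind. If staff now apply 'or' literally, moving to 'and' would cost patients in that group, and the documents cannot say how many. If staff already read it as 'and', nothing is lost. In either case, the patients removed fail a limit that the protocol itself sets.

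The objection that a one-word swap would exclude 130/58 with pulse 80 is correct and is met by the systolic-only wording.

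**Conclusion.** The concern holds. The only numeric stability rule in the visible text excludes patients only when they fail both limits, and it admits readings such as 80/45 with pulse 100 that do not fit a pathway meant for stable patients. That 'and' was intended is an inference from the triage, setting and discharge text, but a well-supported one.

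The severity is modest. The criterion is applied before randomization in both arms, so it does not bias the comparison between them, and no power or error-rate figure changes. Clinical judgement would probably stop many of the affected patients. Their number cannot be derived from the documents. The conclusion rests on reading the criterion as it stands and on the omitted figures not containing a different limit.

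**What to change.** In Section 6, require both limits at the time of consent, so that failing either makes the patient ineligible. The smallest change is 'and' for 'or'. If an isolated diastolic value just under 60 should not exclude a patient, use: *Hemodynamically stable (i.e. systolic blood pressure >100 and pulse <110 at the time of consent)*. Whether to drop the diastolic limit is a clinical decision for the investigators.

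Refer to this definition where Sections 11 and 22 say 'stable', and record both values as checked before the envelope is opened.

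The cost is one line in Section 6 and two cross-references. The downside is some loss of eligible patients, of unknown size. It matters most for hematemesis, so the investigators should check ED records for how many such patients fail one limit only.

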10. STUDY ENDPOINTS*

- The primary endpoint will be time to detection of active bleeding or stigmata of recent bleeding [blood clot or visible vessel].
- Secondary endpoints will include, admission rate, hospital length of stay, number of invasive procedures, blood product transfusions, number of therapeutic procedures, complication rates, costs of admission, and readmission rates

11. PROCEDURES INVOLVED*

Screening

- Patients presenting to the Emergency Room with H or NHGIB (defined as hematemesis, or melena or hematochezia respectively or severe anemia) will be identified by a member of the ED staff and triaged to the CDU for stable patients or ICU for unstable patients.

Once a subject is identified a page will be sent to a member of the research team (i.e, research staff member, GI fellow on call, or GI attending on call) from the CDU. In addition to this, the clinical research coordinator and or GI fellow will screen the Emergency Department triage software for patients who are listed as having NHGIB. Based on prior experience of our randomized trial we expect for every 3 patients asked to participate in the study, there will be 1 patient who agrees to participate. In the Emergency Department study already cited, the Emergency Department at UMass sees about 350 patients annually for GI bleeding. Of these patients, approximately 230 patients have NHGIB and 120 have hematemesis. Given the 3:1 screening ratio, we would expect approximately 40 to be enrolled for the H and 40 patients for the NHGIB patients every year who agree to participate in the study. In 24 months, we would expect to recruit up to 160 patients to our study, 80 for the H and NHGIB respectively. Once a subject is identified the subject will then be seen and examined by the GI fellow and attending as per standard of care and asked to participate in the study.

[figure not shown]
Randomization:

- If inclusion/exclusion criteria are met, the consent discussion takes place and only if the subject agrees and consent is obtained, then the subject is randomized to the “Early Capsule Group” or “Standard of Care Group.” All patients in the “Early Capsule group” will receive the video capsule. A few of the patients in the “Standard of Care Group” may receive the capsule as indicated by what is considered the standard workup.

INVESTIGATOR STUDY PLAN - H00015196

- We will assign patients to study ID numbers consecutively by the order of which they are enrolled in our study. For the Randomization Process we will be utilizing a random sorting generator to assign integers in a random order, corresponding to study IDs which allows researchers to randomly assign study participants into specific study groups. The same process would apply to the H and NHGB groups, but each of these groups will have separate randomizations. Assignments are put into a mail merge, locked with a password, and printed, then put into a sealed, security envelope, which is sealed with a Study ID sticker. The Randomization Scheme will allow us to attach particular Study ID numbers randomly to particular groups based on our criteria to have 40 subjects in the early capsule group and a comparable number in the Standard of Care SOC workup arm for both the H and NHGIB groups. The envelope is only opened once all entry criteria have been met and the subject will be assigned a group/arm. Subjects with a Study ID ending in 1-80 will be enrolled in the H group. Subjects with a Study ID ending in 100-180 will be enrolled in the NHGIB group.
- We plan to enroll up to 160 subjects in our study. 40 subjects will be randomized to the “early capsule” deployment group and 40 in the SOC arm for H patients. A similar allocation will apply to the NHGIB group with 40 patients in each arm. This means that this group of subjects will have a VCE deployed as soon as possible after presentation to the ED and CDU, once the consent process has taken place, eligibility has been confirmed, and the subject has met the standard of care guidelines for preparation before capsule ingestion. Standard preparation for capsule ingestion means that a patient cannot eat for 10 hours prior to deployment of the capsule. Therefore, patients in our study will be asked when they had last eaten. If patients report that they have not eaten anything over the past 10 hours we will deploy the capsule immediately. If, however, patients say that they have eaten something over the past 8 hours we will take note of when they believe they last ate and will deploy the capsule 8 hours after the time that they last ate. In our previous ED study, no patients in the early capsule arm had food in the stomach on capsule examination.

INVESTIGATOR STUDY PLAN - H00015196

[figure not shown]

All medications in the study, erythromycin and metoclopramide and those used for conscious sedation during endoscopy are FDA approved

All procedures in the study are used in a conventional manner and are devices are all FDA approved. Risks of endoscopy include sore throat, bleeding, perforation and infection. Conscious sedation risks are hematoma during placement of an IV, over sedation, aspiration and pneumonia.

Procedures

INVESTIGATOR STUDY PLAN - H00015196

Capsules are swallowed with a small [4-12 oz.] amount of water. As noted above, patients will not have the capsule deployed until it has been confirmed that 10 hours have passed since the patient had last eaten. Patients are allowed to take medications up to two hours prior to ingesting the capsule (which is standard of care).

Immediately following ingestion of the VCE a research staff member will use the capsule's Real-Time Viewer (RTV) to inspect for blood in the stomach. If blood is found in the stomach, the recording will be stopped. At 40-60 minutes following VCE

INVESTIGATOR STUDY PLAN - H00015196

ingestion, a staff member will again use the RTV to confirm that the capsule has entered the small bowel. If the capsule at that time is still in the stomach a prokinetic agent (either metoclopramide or erythromycin, [these agents are commonly used in patients with upper GI bleeding to help get blood clot out of the stomach prior to upper endoscopy to help clear the stomach to improve the chance of finding the source of bleeding]. Based on experience the need for either prokinetic agent is in approximately 1 out of 8 patients. If a prokinetic agent is required a staff member will check within another 40-60 minutes to again verify that the capsule has moved to the small intestine. No further prokinetic will be given. For the H group the recording will be stopped after the small bowel has been entered. For the NHGIB group four to 5 hours after ingestion, a staff member will use the RTV to again check for blood. This is the mean small intestinal transit time of the small intestine. If the VCE is in the cecum, the recording will be stopped and data will be downloaded to the workstation and processed into a video. If the VCE has not reached the cecum, at four and eight hours after ingestion, a staff member will again check the RTV to see if blood is present and/or the ileocecal valve has been passed. Data from the capsule recorder will be downloaded to a workstation as soon as possible. Battery life for the EC-10 capsule is now >12 and up to 20 hours

The PI or sub-investigator will then view the video of the capsule recording [it takes about 5 minutes to establish if there is bleeding and where it is coming from. More detailed analysis will take about 15-20 minutes]. As soon as the capsule recording has been reviewed, the PI or sub-investigator will inform the patient's attending gastroenterologist on the consult service as to where the bleeding is coming from or that bleeding is not seen, as soon as possible after the video has been reviewed. Depending on the findings a recommendation will be made as to the next most appropriate test. See attached Figure 1. If blood is found in the esophagus, stomach or duodenum an upper endoscopy is recommended. If blood is seen in the small intestine, it will be recommended that the subject next have a push enteroscopy, deep enteroscopy, or angiography. If blood is found in the right colon, colonoscopy may be performed or deferred to colonoscopy as an outpatient, if active bleeding has ceased. If the capsule study is not diagnostic and no blood is seen in the GI tract and there is no ongoing hematochezia, the subject will be placed in ED observation for up to 23 hours and evaluated for potential discharge and follow-up by gastroenterology as an outpatient. If, and as appropriate an EGD or colonoscopy will be performed as an outpatient within 72 hours.

For most subjects, the capsule will pass in a bowel movement within 24 -72 hours of ingestion.

An equal number of subjects [up to 40] will be randomized to the "SOC group." For NHGIB workup may include upper endoscopy, colonoscopy, and additional capsule or small bowel enteroscopy depending on the subject's presentation and the results of the workup performed by the gastroenterology team. For some subjects, the VCE would be done as part of standard of care. We estimate that 4-10% of patients will have small intestinal bleeding. For patients requiring a video capsule endoscopy as part of "SOC workup" the patients will be given the same Olympus video capsule that is used in the "Early Capsule" group. Further management would be as standard of care which requires

INVESTIGATOR STUDY PLAN - H00015196

admission. These subjects will be discharged on the recommendation of the attending hospitalist after completion of treatment.

Review and Follow-Up

During hospitalization, data will be recorded from ED pulse check, and EPIC regarding fluid administration, transfusion of pRBC, initial hematocrit, times and types of procedures (e.g. upper endoscopy, enteroscopy, colonoscopy etc), time from entry to ED and CDU, to time to localization of source of bleeding, admission disposition discharge from CDU, regular floor, ICU), time of discharge. The procedures involved in the hospitalization (i.e. upper endoscopy, enteroscopy, and colonoscopy) will be done as part of standard of care. All of this information will be linked to the subject's study ID number as described above. This data collection is for research purposes only.

In addition, the costs of the procedures will be collected through financial services. The costs that will be collected are both the fixed and variable costs associated with each patient in the study. We will also collect the direct and indirect costs allocated to each patient. All charges associated with the admission for each patient in the study will have costs allocated. This will be evaluated as an additional data point to compare the two arms of the study. No additional PHI will be collected.

Telephone Follow-Up

Those subjects discharged from the CDU will be contacted the following day by phone by a research staff member to make sure that they are doing well and that the appropriate follow up procedure has been arranged. Each patient will be called 30 days after discharge to check to see if bleeding has recurred. Please see attached form for telephone script that staff member will read along with particular questions that will be asked.

No more than three attempts will be made at each time point to reach the subject. If a message is left, it will be "Hello, this is [name] calling from UMass looking to speak with [subject]. Please call back at [number] at your earliest convenience. Thank you."

